Attachment D provides the text of the online surveys we will administer.

EHR data (all available data through end of follow-up will be extracted in the following domains)

Basic demographics

Diagnoses

Encounter characteristics

Provider characteristics

Blood pressure

Medications

Lab results

Death indicator

The EHR data analysis section, below, provides additional detail.

HBPM device data (all available measurements made during follow up, for Arm 1 only)

Blood pressure

Heart rate

Primary BP control outcome: The following pre-specified outcome will be used for the primary test of comparative effectiveness:

- 1) Reduction in SBP at 6 months. Reduction is defined by the absolute difference between the eligibility SBP (collected from the patient at the time of eligibility assessment), and the SBP measured at the most recent outpatient clinical encounter 6 months after enrollment. If more than 1 measurement is recorded during a single clinical encounter, the lower/lowest will be used.

Primary patient satisfaction outcome: The following pre-specified outcome will be used for the primary test of patient satisfaction:

- 2) Net Promotor Score. This score is assessed by asking a single question about likelihood of recommending the device to a friend, with options from 1-10 (10 being extremely likely). As per published methods^{7,8}, persons indicating 9 or 10 are considered "Promotors"; persons indicating 7 or 8 are "Passives"; and persons indicating 1-6 are

“Detractors”. The score is calculated by taking the percent of Promotors and subtracting the percent of Detractors, yielding a score for each group ranging from -100 to 100. Note that an identical score could theoretically be produced for a group with either a relatively high proportion of Promotors and Detractors, or a relatively low proportion of both.

Exploratory outcomes: The following pre-specified secondary outcomes will also be measured and analyzed. These include alternative measures of BP control, other patient-reported outcomes, and process measures intermediate along the causal pathway to BP control.

- 3) Documented attainment of a 10 mmHg reduction in SBP from baseline to 6 months, as defined above.

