- 4) Documented attainment of a 10 mmHg reduction in SBP at 6 months, as in Outcome 1, but assessed using home BP measurements, when available. As per guidelines, a set of 12 or more home measurements (counting no more than 2 in the morning and 2 in the evening of each day) within any given 1 week time period will count as a completed Home Measurement Protocol¹². The average SBP and DBP measurements within the most recent completed Home Measurement Protocol within 180 days of the index date (e.g., 6 months after enrollment) will then be used as the attained BP, regardless of subsequent clinic measurements or subsequent random home measurements. If no completed Home Measurement Protocol is available within 180 days of the index date, the most recent clinic measurement will be used. Note that a documented Home Measurement Protocol can only be attained in Arm 1, as home measurements will not be accessible in Arm 2.
- 5) Other BP Control outcomes defined as ((SBP<140 mmHg and DBP<90 mmHg) OR (SBP<130 and DBP<80) OR 10 mmHg reduction), assessed using the baseline measurement (self-reported OR last clinical measurement prior to randomization from the electronic health record) and subsequent measurements (clinical measurements OR clinical + home measurements) at a specified time-point (6 OR 12 OR 18 months) or using a time-to-control approach.
- 6) Patient reported outcomes including various aspects of satisfaction with the HBPM device and BP management, including quality of shared decision-making and patient activation.
- 7) Visit frequency. We will analyze the number of ambulatory care visits during the 6 month follow up period; we will also analyze the number of visits made before attainment of the first in-control BP.
- 8) Medication intensification. We will analyze the proportion of clinical visits with high BP (SBP>140 mmHg or DBP>90 mmHg) after which a BP medication was added.

Pre-specified subgroups: The following subgroups are pre-specified:

- Baseline Age: 20-44 vs 45-64 vs. 65+ years
- Sex: Male vs. Female vs. Other vs. Missing
- Race/Ethnicity: Non-Hispanic White vs. Non-Hispanic Black vs. Non-Hispanic Asian vs. Hispanic (any race) vs. Other/Multiple vs. Missing
- Subjective Social Status, measured through online survey at baseline, using MacArthur Scale for SES (not the “Community” version)⁹: Upper vs. Middle vs. Lower tertile, defined within our recruited sample of participants

Analysis Plan

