Exploratory analyses: We plan to analyze many additional outcomes, including alternate methods of defining BP control, alternate time-points, and additional endpoints including patient-reported outcomes and BP control process measures. These analyses are not planned for testing of the primary hypotheses, but are important for describing the experience of BP control using the two different device types and for generating hypotheses for future study. Our general approach to these analyses will be similar to how we approach the primary and secondary analyses, but we may use other methods that are not pre-specified.

EHR data analyses: We plan to analyze the EHR data obtained from each partner site. Each partner's EHR information is standardized to the PCORnet Common Data Model (CDM) to collect data from the EHR systems. The PCORnet CDM is a HIPAA Limited Data Set and quality checks of the EHR data are performed using procedures and algorithms that PCORI established

for its clinical data research network sites. Among other things, it standardizes laboratory tests and results using LOINC for laboratory tests and medication data using RxNorm.

Queries will be sent to the sites asking for the following data:

- Ambulatory Clinic information, including:
- Basic demographic and visit information
- Diagnoses
- Medication orders
- Blood pressure and pulse measurements
- Lab Reports relevant to blood pressure
- Vital Status

To obtain the information above, we will use the following tables from the PCORnet CDM:

- DEMOGRAPHIC
- ENCOUNTER
- PROCEDURE
- VITAL
- PRESCRIBING
- DIAGNOSIS
- LAB_RESULT_CM
- DEATH
- DEATH_CAUSE

Please note that the research team will NOT request release of information pertaining to drug and alcohol abuse, diagnosis or treatment; HIV/AIDS testing; genetic testing; or mental health diagnosis or treatment.

Attachment E summarizes the steps required for the OneFlorida Data Trust to obtain data for the queries.

Enrollment prediction modeling:

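### Outcome 4 and the clinic-plus-home versions of Outcome 5 use home BP from one arm only, so they can differ between arms when the devices work equally well; the clinic-only versions should carry the comparison

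*Combined protocol and SAP*

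**What the plan says.** The Measurements section lists device readings as "HBPM device data (all available measurements made during follow up, for Arm 1 only". Outcome 4, under Exploratory outcomes, is attainment of a 10 mmHg SBP reduction at 6 months using home BP where available. A completed Home Measurement Protocol needs at least 12 readings within a week. Its average "will then be used as the attained BP, regardless of subsequent clinic measurements or subsequent random home measurements". The fallback is: "If no completed Home Measurement Protocol is available within 180 days of the index date, the most recent clinic measurement will be used". The plan then adds that "a documented Home Measurement Protocol can only be attained in Arm 1, as home measurements will not be accessible in Arm 2".

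Outcome 5 allows several definitions of control, among them a choice of follow-up source: "subsequent measurements (clinical measurements OR clinical + home measurements". It can be assessed at 6, 12 or 18 months or as time to control.

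The clinic rule, set under the primary BP control outcome, differs in kind: "If more than 1 measurement is recorded during a single clinical encounter, the lower/lowest will be used". Outcome 3 is the clinic-only counterpart of Outcome 4: "Documented attainment of a 10 mmHg reduction in SBP from baseline to 6 months, as defined above".

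On analysis, the Exploratory analyses paragraph says: "Our general approach to these analyses will be similar to how we approach the primary and secondary analyses". The same sentence leaves room for methods that are not pre-specified. The paragraph also says these outcomes do not test the primary hypotheses.

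**The concern.** Randomisation makes the arms comparable, but only if the outcome is measured the same way in both. Here it is not:

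- **Source.** Arm 1 completers are scored on home BP. Arm 1 non-completers and all of Arm 2 are scored on clinic BP.
- **Summary rule.** The home value is an average of 12 or more readings. The clinic value is the lowest reading of an encounter.
- **Timing.** A home week can override a later clinic reading.
- **Baseline.** Outcome 4 refers back to Outcome 1, whose baseline is the participant-reported clinic SBP at eligibility. A completer's change is therefore clinic baseline minus home follow-up, and any home–clinic offset goes straight into the 10 mmHg threshold.
- **Opportunity.** In a time-to-control analysis, home readings added to clinic readings give Arm 1 more occasions to record a first controlled value.

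The plan discloses the imbalance but draws no consequence from it. It sets no calibration and does not limit these versions to description. At stake is a device effect reported on a BP-control endpoint that is wholly or partly a measurement effect. Labelling the outcome exploratory warns about chance findings; it does not remove a systematic difference.

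**Working it through.** **Plan's own figure.** The Sample size justification gives 80% power for 0.125 SD with 1000 per arm (11 vs 10 mmHg, SD 8). Assuming two-sided 0.05, power = Φ(0.125 × √500 − 1.96) = Φ(2.795 − 1.960) = 79.8%, so it reproduces. It concerns the clinic-based primary outcome and is not affected by this point.

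**Fixed time-point: inputs.** From the plan: 1000 per arm, and the example SD of 8 mmHg. Assumed: no true device effect; clinic attainment 50%; a wider SD of 16 as an alternative; share of Arm 1 completing the home protocol f = 30% or 50%; offset d (clinic minus home) from −3 to 8 mmHg.

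**Formula.** Arm 2: p2 = 0.5. Arm 1: p1 = (1 − f) × 0.5 + f × Φ(d/SD). The shift is p1 − p2 = f × [Φ(d/SD) − 0.5].

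Example: d = 3, SD 16, f = 0.5 gives 0.5 × (0.574 − 0.5) = +3.7 points.

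Shift in percentage points, Arm 1 minus Arm 2:

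| SD | f | d = −3 | 0 | 3 | 5 | 8 |
|---|---|---|---|---|---|---|
| 16 | 50% | −3.7 | 0 | +3.7 | +6.1 | +9.6 |
| 16 | 30% | −2.2 | 0 | +2.2 | +3.7 | +5.7 |
| 8 | 50% | −7.3 | 0 | +7.3 | +11.7 | +17.1 |
| 8 | 30% | −4.4 | 0 | +4.4 | +7.0 | +10.2 |

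For the first row, a two-sided 5% z-test would reject in 38%, 5%, 38%, 79% and 99% of trials although the devices are identical.

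**Zero offset, unequal spread.** Averaging may narrow the home SD. With assumed SDs of 12 (home) and 16 (clinic) and f = 0.5, the shift is 0.5 × [Φ((16/12) × Φ⁻¹(p2)) − p2]:

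- p2 = 0.4: 0.5 × (0.368 − 0.4) = −1.6 points
- p2 = 0.6: 0.5 × (0.632 − 0.6) = +1.6 points

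So equal means alone do not guarantee a fair comparison.

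**Time to control.** This was simulated as ever recording SBP < 140 (the threshold is the plan's). Assumed: true SBP mean 142, between-person SD 12; two clinic readings with noise SD 9; four home averages with noise SD 4, added to the clinic readings. Simulated figures are good to about 0.1 point.

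| Scenario | Clinic only | Clinic + home | Gap at f = 100% / 50% / 30% |
|---|---|---|---|
| Zero offset | 58.6% | 67.0% | +8.4 / +4.2 / +2.5 |
| Home 3 mmHg higher | 58.6% | 63.3% | +4.7 / +2.4 / +1.4 |
| Zero offset, lowest of two clinic readings per visit (within-visit SD 5, total noise SD 9) | 65.7% | 70.6% | +4.9 / +2.5 / +1.5 |

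If home readings are added and any qualifying reading counts, the first controlled value can only come sooner, so the gap favours Arm 1 at any offset.

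If home averages replace clinic readings instead, that argument fails. Two home averages in place of two clinic readings, at zero offset, give 50.8% against 58.6%, which is 7.8 points against Arm 1 at full completion. Outcome 5 does not say which combination is meant.

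**Clinic only in both arms.** With identical devices and the same visit pattern, the expected difference is 0 and the rejection rate is 5%, whatever the offset or completion rate.

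**The case against.** The strongest reply is that the plan already states the imbalance, calls these outcomes exploratory and hypothesis-generating, keeps the primary outcome on clinic BP, and contains clinic-only counterparts. It also does not commit to a particular between-arm test here, since it reserves methods that are not pre-specified. All of that is true, and it is why the point ranks low. It does not settle the matter, because nothing tells the analyst or reader that a between-arm contrast on these versions cannot be taken as a device effect.

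Other points stand in part:

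- At a fixed time-point neither sign nor size is known, and the equal-spread model gives exactly zero at zero offset. The documents offer no basis for assuming that case.
- The time-to-control direction depends on home readings being added to clinic readings, as shown above. The simulation also ignores DBP, which both threshold definitions require, and models ever-controlled status instead of time.
- Clinic-only versions are not immune to everything. If visit frequency (Outcome 7) differs by arm, clinic-only time to control can be affected. They do, however, apply one rule to both arms.
- Calibration is possible in principle, because Arm 1 has both clinic and home BP. It would need an offset estimated in self-selected completers and applied by assumption, so it suits a labelled sensitivity analysis better than the main comparison.

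Separately, the Measurements overview attributes device readings to Arm 2, against the Study Interventions section, the device-data list and Outcome 4. The passages should be reconciled. Either way only one arm supplies home data.

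**Conclusion.** The concern holds. It follows from the plan's own definitions that Outcome 4 and the home-inclusive versions of Outcome 5 score the arms by different rules, so a difference can arise with identical devices. Under the assumed inputs, a 3 mmHg offset in either direction moves fixed-time attainment by about 2 to 7 points, and an 8 mmHg offset by about 6 to 17. Adding home readings to time to control moves it by about 1.4 to 8.4 points towards Arm 1. These are illustrations, since the offset, completion rate and home SD are not in the documents. The primary tests, Outcome 3 and the clinic-only versions of Outcome 5 do not use home data and are untouched. This is a worthwhile clarification for exploratory outcomes and does not endanger the trial's main conclusions.

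**What to change.** State in the SAP that between-arm BP-control comparisons, including time to control, use only clinic/EHR readings selected by the same rule in both arms: Outcome 3 and the clinic-only versions of Outcome 5. Report Outcome 4 and the home-inclusive versions of Outcome 5 descriptively within Arm 1, without a between-arm estimate or p-value. No clinic-only version of Outcome 4 is needed, because it would be identical to Outcome 3. Correct the arm label in the Measurements overview at the same time.

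The cost is wording only, with no new data. What is lost is an exploratory contrast in which device effect and measurement source cannot be separated; home BP is still reported for Arm 1.

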We have designed a patient-level randomized controlled trial that will compare the effectiveness of Smartphone-linked versus standard HBPM for helping patients with uncontrolled hypertension achieve a reduction in their SBP, and patient satisfaction with the device. We aim to enroll 2000 patients who will be randomized in a 1:1 ratio to receive a Smartphone-linked or standard HBPM. We will use data from the electronic health record (EHR), an online patient portal, and the home BP monitor (in the Smartphone-linked arm) to collect outcome data for a period of at least 6 months (for the primary outcome), and up to 18 months (for secondary outcomes, depending on enrollment date). The primary BP control outcome will be reduction in SBP, by clinic measurements, at 6 months. The primary patient satisfaction outcome will be the Net Promotor Score^{7,8}, derived from self-reported likelihood of recommending the device to a friend, at 6 months.

Study Subjects

Target population

Adults receiving medical care who have uncontrolled BP

Accessible population

Adults receiving medical care at a participating PCORnet institution who meet inclusion criteria, are willing to enroll in the study, and complete baseline surveys.

Inclusion Criteria

- Age \geq 18 years
- At least one ambulatory visit in one of the participating study sites during the past year
- SBP > 145 mmHg at most recent clinic visit (may be treated with BP meds already or not), as reported by the participant
- A self-reported commitment to “work on lowering your blood pressure by 10 points or more to reduce your risk of heart attack and stroke”
- Owns a Smartphone (Android or iOS) and has an email address
- Willing to receive text messages from the study
- Can read/write English well enough to use English-based Smartphone apps and fill out online surveys in English

Exclusion Criteria

- Has an arm circumference <22 cm or >42 cm
- Owns a functioning HBPM and has used it in the last 3 months

Recruitment Plan

Participating sites will recruit patients via 2 basic methods.

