Overview: Our primary analyses will test two independent hypotheses: that SBP reduction (outcome 1, defined above) differs by study arm, and that promotion of the HBPM device (outcome 2) differs by study arm. Subgroup analyses and exploratory outcomes will also be analyzed, as described below.

Primary BP control analysis: For analysis of this outcome, which is continuous (defined above), we will use a random effects linear model, including a random effect for clinic and a fixed effect for a 3-level variable that indicates whether the clinic is participating in a concurrently-running cluster-randomized quality improvement trial (Not participating vs. Full Support MAP intervention^{13,14} vs. Self-Guided MAP intervention^{13,14}).

Primary patient satisfaction analysis: The Net Promoter Score (NPS) is calculated from the proportions of Promoters and Detractors, as described above. To assess the influence of treatment assignment and other exposures on the NPS, we will first define the 3-level outcome classifying each participant as a Promoter, a Passive, or a Detractor, then fit a random effects multinomial logistic model for the independent effect of the exposure on this outcome. The model will include the same random and fixed effects specified for the primary BP control analysis. Expected proportions in each outcome group by treatment assignment will then be obtained using standardization. Finally, the NPS scores for each group, as well as the between-group difference in the score, with 95% confidence intervals for each, will be calculated as linear combinations of the adjusted proportions, and a p-value calculated assuming a null hypothesis of no between-group difference in the NPS.

Subgroup analyses: We will produce subgroup-specific analyses of the primary outcomes for each of the pre-specified subgroups, and test for heterogeneity by including the appropriate interaction terms in the models described above, with an omnibus test for each of the 4 grouping variables. Subgroups that include fewer than 100 study participants or with missing values for the subgrouping variable will be omitted from the omnibus test and results presentation. P-values for within-subgroup treatment effects will be reported only if the omnibus test is statistically significant at P<0.05.

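### The exploratory 6-month visit count has no named model or covariates; pre-specifying each participant's prior visit count would probably sharpen it at almost no cost

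*Combined protocol and SAP*

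**What the plan says.** Visit frequency is item 7 under Exploratory outcomes: "We will analyze the number of ambulatory care visits during the 6 month follow up period". A second count, of visits made before BP first comes under control, is listed in the same item. Neither has a stated model, distribution or covariate set.

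The method has to be taken from Exploratory analyses in the Analysis Plan, which says the approach will be "similar to how we approach the primary and secondary analyses, but we may use other methods that are not pre-specified". The approach referred to is set out under Primary BP control analysis: a random effects linear model "including a random effect for clinic and a fixed effect for a 3-level variable", the 3-level variable being the clinic's status in the concurrent MAP quality improvement trial. Both named terms describe the clinic, not the participant.

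On data, the EHR list under Measurements includes encounter characteristics and says "all available data through end of follow-up will be extracted in the following domains". EHR data analyses requests the ENCOUNTER table. The Measurements overview uses EHR data for baseline conditions as well as outcomes, and item 5 allows the last clinic BP before randomisation to come from the EHR. The inclusion criteria require "At least one ambulatory visit in one of the participating study sites during the past year". No start date for the extract is given.

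On status, Exploratory analyses says "These analyses are not planned for testing of the primary hypotheses", and Multiple hypothesis testing describes these outcomes as hypothesis-generating.

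**The concern.** How often a patient attends clinic tends to persist over time, for reasons such as comorbidity and access to care. A model with only clinic-level terms leaves the participant-level part of that variation in the error of the arm comparison. The pre-randomisation count of the same quantity would remove some of it. It would also remove chance imbalance between arms in heavy attenders, who weigh strongly in a skewed count.

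What is at stake is the precision of one descriptive process measure. The protocol places it on the causal pathway to BP control, and a clinic visit is also the occasion on which follow-up SBP is recorded, so a tighter estimate of whether the device changes attendance is useful background. If the covariate is left to be chosen after the data are seen, the adjusted result is also open to the charge of selective adjustment.

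**Working it through.** **Inputs**
- 1000 per arm, standardised effect 0.125 SD, stated power 80% (Sample size justification). These are given for SBP reduction. The plan states no effect size or power for visit counts, so they serve here only as a yardstick.
- Two-sided 5% significance: assumed, since the sample-size paragraph states no alpha.
- rho, the within-clinic correlation between prior and follow-up visit counts: not in the documents, so shown as a range.
- Complete EHR linkage: assumed.

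**Step 1. The plan's own figure**

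Power = Phi(0.125 × sqrt(1000/2) − 1.96) = Phi(2.795 − 1.96) = Phi(0.835) = 79.8%, against 80% stated. The plan's figure reproduces.

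**Step 2. Adding the covariate**

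Residual variance is multiplied by (1 − rho²), so power = Phi(2.795 / sqrt(1 − rho²) − 1.96). The equivalent unadjusted sample is 2000 / (1 − rho²).

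| rho | Variance factor | Variance cut | SE ratio | Power at 0.125 SD | Equivalent total n |
|---|---|---|---|---|---|
| 0 | 1.00 | 0% | 1.000 | 79.8% | 2000 |
| 0.2 | 0.96 | 4% | 0.980 | 81.4% | 2083 |
| 0.3 | 0.91 | 9% | 0.954 | 83.4% | 2198 |
| 0.4 | 0.84 | 16% | 0.917 | 86.2% | 2381 |
| 0.5 | 0.75 | 25% | 0.866 | 89.8% | 2667 |

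**Step 3. Which rho is plausible?**

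This rests wholly on assumed visit rates. Take gamma-Poisson counts with mean 4 in the prior 12 months, mean 2 in the 6-month follow-up and gamma shape 3.
- Correlation of the raw counts: about 0.48.
- Restricting to participants with at least one prior visit, as eligibility requires, and entering log(1 + count): about 0.43.
- If clinics carry 20% to 40% of the variance in visit rates, which the clinic random effect already absorbs, the within-clinic correlation is about 0.38 to 0.31. Step 2 then gives 85.6% to 83.6%, a gain of roughly 6 to 4 points.

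More dispersed rates (mean 2 or 3 visits per 6 months, gamma shape 0.7 to 2, no clinic effect, no eligibility restriction) give correlations of 0.67 to 0.80. In simulation the variance of the log rate ratio then fell to between 0.33 and 0.63 of its unadjusted value. The direction is the same throughout; the size depends on the assumptions.

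**The case against.** The strongest reply is that the plan contains no error here. Item 7 is exploratory, has no target difference, power claim or decision rule, and is unbiased by randomisation whether or not it is adjusted. Which precision covariate to use for one of many exploratory outcomes is a matter of preference. That stands, and it limits the point to an optional refinement.

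A reader might infer that the plan has decided against adjustment. The documents do not support this: item 7 is silent, and the sentence that sets the default also leaves room for methods not named in advance. What remains is that no covariate is committed to.

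A reader might take the prior counts as already in hand. They very likely are, but the extract has a stated end and no stated start, and one pre-randomisation BP reading for item 5 does not guarantee a full 12-month visit history.

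A reader might quote the power figures as the power of the visit analysis. They are not, because the 0.125 SD belongs to SBP. The larger gains also ignore variation that the clinic effect already absorbs, so the within-clinic correlation is the one to use.

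Finally, the same covariate might seem to serve the other count in item 7. No calculation here supports that. That count stops at an event and is censored or undefined for participants who never reach control, so it raises separate questions.

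**Conclusion.** The point holds as a minor, optional improvement. Under the stated default, the 6-month visit count would be compared between arms with clinic-level terms only, although a participant-level predictor is very likely available. The comparison is valid but probably less precise than it need be. The variance saving is about 9% to 25% for a within-clinic rho of 0.3 to 0.5. Allowing for the eligibility rule and for clinic effects under the assumed visit rates, the lower part of that range is the more cautious expectation.

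The conclusion assumes that visit frequency persists within patients, that the EHR query reaches back before randomisation, and that linkage is complete. It is not a finding of bias. It has no bearing on the SBP or Net Promoter comparison, since neither contrast depends on how precisely visit frequency is estimated.

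**What to change.** Add one sentence to the Analysis Plan. For the 6-month ambulatory visit count, the model will include the participant's number of ambulatory visits at participating sites in the 12 months before randomisation, for example as log(1 + count), derived from the ENCOUNTER table with the same visit definition as the outcome, alongside the clinic and MAP terms. State in the EHR query that it covers that 12-month look-back. Leave the count of visits before first control outside this change.

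The cost is one derived variable and a stated query window, with no new contact with participants. Visits outside participating sites will be missed; this weakens the covariate but does not bias a randomised comparison. If the covariate proves weakly prognostic, almost nothing is lost with 2000 participants.
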